5.5 Accountability Procedures

Clinic records will be maintained to capture the following information:

- a) Quantity received,
- b) The current quantity on site,
- c) Quantity used on each subject,
- d) Quantity removed from stock but not dispensed (e.g., damaged, dropped, spilled), and
- e) Quantity remaining at the end of the study and retained, returned, or destroyed, as per the sponsor’s instructions.

5.6 Method of Assigning Treatments

All patients enrolled in the study will receive similar treatment. There is no blinding of treatment assignments.

6. STUDY PROCEDURES & ASSESSMENTS

6.1 Study Procedures

6.1.1 Screening (Day -28 to -1)

Patients may be enrolled in the study at or any time after initial presentation if it can be documented that they comply with all inclusion and exclusion criteria. (Enrollment day is designated as Day 0.) The investigator or designee will discuss with each subject the nature of the study, its requirements, and its restrictions. Written informed consent will be obtained prior to the performance of any protocol-specific procedures

The following will be required during the Screening period to determine eligibility:

- Informed consent
- Subject demographics
- Medical history
- Review of concomitant medication
- Relevant physical examination
- Vital signs
- Clinical laboratory tests
- Hepatitis B, Hepatitis C, and HIV screening
- Review of inclusion and exclusion criteria and study restrictions

6.1.2 Enrollment (Day 0)

After enrollment and an initial assessment including the Leg Ulcer Measurement Tool [LUMT] (see Appendix 4), patients will be treated with DermGEN decellularized human dermal matrix. Following standard of care procedures, the wound will be debrided to provide healthy tissue margins and a bleeding wound bed. A 4 cm x 4 cm piece of DermGEN will be prepared by sizing to approximately 2-3 mm past the margins of the ulcer and securing to the wound with sutures ensuring that the dermal side is in contact with the wound bed. [*The dermal side of DermGEN can be identified by the following: (i) apply a drop of blood or contact with blood from the wound bed to one surface of the graft; (ii) rinse blood off with sterile saline; (iii) if blood does not wash off entirely, this is the dermal side—the epidermal side will not retain visible quantities of blood.*] A non-adherent dressing will be used to cover the DermGEN graft, followed by (a) a moisture retentive dressing and a compressive dressing, or (b) dressings as specified for use by all patients, once the first 1 to 3 patients have been treated (see section 3.1, above). Suitable off-loading will also be provided, with careful instructions for use.

6.1.3 Follow-up Procedures (Week 1 to Week 20)

Follow up visits will be at Weeks 1, 2, 3, 4, and 12 and 20, and as required for clinical care of active detriments to healing and local wound care. The Leg Ulcer Measurement Tool [LUMT] will be completed at each of the Weeks 1, 2, 3, 4, 12, & 20 follow-up visits in order to capture data relevant to the study. In addition, digital photography will be utilized to capture the appearance and size of the ulcer at each visit. The SF-12 survey will be administered at Day 0, and at the Weeks 4, 12 and 20 visits.

Dressing management will follow and a record of all changes will be kept. All patients will receive wound off-loading using a device appropriate to ulcer location.

All post-treatment complications will be recorded on the appropriate case report form. Patients with complications that may be managed by further treatment, for example antibiotic administration or application of one replacement DermGEN graft, will remain in the study.

For any subject who requests study withdrawal or is withdrawn by the investigator, the reason for study discontinuance will be recorded by the Principal Investigator on the appropriate case report form. Stopping treatment or withdrawal from the study will occur when:

- (i) patient is non-compliant with home care regime (e.g. not wearing off-loading cast),
- (ii) presence of recurrent, untreatable infection,
- (iii) patient develops illness after enrollment that may unduly affect ulcer healing,
- (iv) patient requires more than one re-treatment with DermGEN

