3.2 Dose Selection and Use

DermGEN will be applied on Day 0, following the directions for use.

If at a subsequent visit the product material is deteriorating, then the investigator may, at his discretion, remove the remaining product material, prepare the wound bed appropriately, and apply one new DermGEN treatment. In such cases, the remaining course of the study will continue unchanged, and the patient’s last visit will still be at Week 20.

The reasons for any second application of DermGEN must be carefully documented, together with before and after photographs showing the deteriorating specimen in situ before removal and also the new specimen in place prior to applying new dressings.

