4.6.2 Subject Withdrawal

Any subject who voluntarily withdraws (e.g., withdrawal of consent) or is discontinued (e.g., as a result of an AE) from the study prior to the completion of all assessments will be considered as having withdrawn from the study.

Subjects may be withdrawn from the study under any of the following circumstances:

- (i) patient is non-compliant with home care regime (e.g. not wearing off-loading cast),
- (ii) presence of recurrent, untreatable infection,
- (iii) patient develops illness after enrollment that may unduly affect ulcer healing,
- (iv) patient requires more than one re-treatment with DermGEN

When an event such as a family emergency, a transient intercurrent illness (such as a cold) unrelated to study medication, or a remediable act of non-compliance prevents a subject from participating in a scheduled visit but the subject wishes to continue in the study, then with the agreement of the investigator, the clinical staff may attempt to reschedule the visit and retain the subject in the study.

If a subject is prematurely discontinued from participation in the study for any reason after treatment has begun, the investigator or designee must make every effort to perform the assessments scheduled for the Follow-Up Visit (section 6.5.1). The reason for withdrawal will be recorded in the CRF and the subject's medical record.

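### Sections 4.6.2 and 6.1.3 do not keep patients who meet four criteria linked to poor healing on the visit schedule, so Week 12 and Week 20 values can be missing for outcome-related reasons

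*Protocol*

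**What the plan says.** Two sections of the Protocol govern patients who run into trouble, using the same four criteria: (i) non-compliance with home care, for example off-loading; (ii) infection that recurs and cannot be treated; (iii) a new illness that may impair ulcer healing; (iv) need for more than one re-treatment.

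- Section 6.1.3 is mandatory and names two actions: "Stopping treatment or withdrawal from the study will occur when" one of these is met.
- Section 4.6.2 is permissive and names one action: "Subjects may be withdrawn from the study under any of the following circumstances".

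Section 4.6.2 also defines withdrawal. A subject who leaves voluntarily, or is discontinued from the study, "prior to the completion of all assessments will be considered as having withdrawn from the study". For a subject discontinued after treatment has begun, the investigator "must make every effort to perform the assessments scheduled for the Follow-Up Visit (section 6.5.1").

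The Protocol does retain some patients. Those with manageable complications stay in (3.1.3, 4.4, 6.1.3). After one replacement graft, "the remaining course of the study will continue unchanged" and the last visit is still Week 20 (3.2). Where a transient illness or remediable non-compliance causes a missed visit, "the clinical staff may attempt to reschedule the visit and retain the subject in the study" (4.6.2).

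On timing, section 6.1.3 says: "Follow up visits will be at Weeks 1, 2, 3, 4, and 12 and 20". LUMT and photographs are taken at each of these visits. For quality of life: "The SF-12 survey will be administered at Day 0, and at the Weeks 4, 12 and 20 visits".

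**The concern.** The four criteria are not neutral with respect to outcome. Criterion (iii) refers to ulcer healing itself, (iv) is repeated graft failure, (ii) is uncontrolled infection, and (i) includes failure to off-load, which is part of the treatment. Patients whose complications can be managed stay in, so the rule acts on those whose problems could not be managed.

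If such patients leave, their later wound area, LUMT and SF-12 values are missing for reasons tied to how they were doing. The summaries at Week 12 and Week 20 then describe a more favourable subset. The study has a single arm, so no control group shows the same loss. An analysis plan can choose how to handle missing values, but it cannot recover visits that were not held. Section 7.1.3.2 says that conclusions may be used to design later efficacy studies, so an over-favourable signal would carry forward.

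**Working it through.** The Protocol states no dropout rate, power or effect size for this point, so there is no figure to reproduce. The check is a reading of the text, followed by an illustration.

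**1. Which action applies?** 6.1.3 offers stopping treatment or study withdrawal and says one will occur. 4.6.2 says study withdrawal may occur. The two can be reconciled (one or the other must happen, and withdrawal is optional), but neither assigns an action to a criterion. Neither says that a patient who only stops treatment remains on the schedule.

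**2. What is owed to a patient who leaves the study?**
- Best-effort exit assessment (4.6.2). It cites section 6.5.1, but section 6 ends at 6.3.2. If 6.1.3 is meant, photographs and LUMT are covered. SF-12 is tied to Day 0 and Weeks 4, 12 and 20, so its place at an exit visit is unclear.
- Repeat HbA1c at the withdrawal visit (6.2.3).
- Follow-up of unresolved AEs and of SAEs (9.3.2, 9.3.5).
- Wound, LUMT or SF-12 assessment at Week 12 or Week 20: none.

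**3. Which outcomes are exposed?**
- Area reduction over 4 weeks (primary): little. Visits are weekly to Week 4, so an exit value in that period lies close to the time point.
- Healing in the first 12 weeks (primary): no change if leavers stay in the denominator as not healed. Section 7.1.1 keeps everyone except the first 1 to 3 patients.
- LUMT and SF-12 (primary, with no time point fixed in 2.1 or 6.3.1): the Week 12 and Week 20 values are exposed. Patients who leave after Week 4 still have Week 4 values.
- Area reduction at 12 weeks (secondary, 2.2 and 6.3.2): exposed.

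A patient who leaves just after Week 4 exits 12 − 4 = 8 weeks before the Week 12 assessment and 20 − 4 = 16 weeks before the Week 20 assessment.

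**4. Illustration for mean Week 12 area reduction.**
Inputs: 15-20 enrolled (3.1, 4.1) and 1 to 3 lead-in patients excluded (7.1.1). Assuming the lead-in patients are among those enrolled, n runs from 15 − 3 = 12 to 20 − 1 = 19.

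Let M be the mean of the n − 1 patients seen, and let the missing patient's reduction be M − D. The mean of all n is [(n − 1)M + (M − D)]/n = M − D/n, so the reported mean is too high by D/n. The values of D below are assumptions; the Protocol gives none.

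| D (percentage points) | n = 19 | n = 12 |
|---|---|---|
| 0 | 0 | 0 |
| 25 | 25/19 = 1.3 | 25/12 = 2.1 |
| 50 | 50/19 = 2.6 | 50/12 = 4.2 |

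If the lead-in patients are additional to the 15-20, n is 15 to 20 and the range for D of 25 to 50 is 25/20 = 1.25 to 50/15 = 3.3 points. These figures are for one missing patient. The median, also planned, would usually move less.

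**The case against.** The strongest case against is that this is loose wording in a small pilot. Section 7.1.2 expects no statistical conclusions and plans descriptive statistics only. Reasons for withdrawal must be recorded, and needing more than one re-treatment is already an informative failure. After untreatable infection or repeated graft failure a patient may move to other care, so a Week 12 area may no longer reflect DermGEN, and non-compliant patients may not attend. The 6.5.1 reference is probably a numbering slip for 6.1.3. All of this stands, and it limits the weight of the point. It does not supply the missing assessments.

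Some stronger readings are tempting, but the Protocol does not support them:

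- **That 4.6.2 turns stopping treatment into withdrawal.** Its definition concerns subjects discontinued from the study. Section 3.1 describes study treatment lasting up to 20 weeks, so stopping treatment while staying in the study is a possible reading, and under it no visits are lost. The fault is that the Protocol does not say so.
- **That nothing is collected after exit.** The exit assessment, HbA1c and AE follow-up are required.
- **That eight weeks of wound data are lost before Week 12.** No patient has a scheduled study visit between Weeks 4 and 12. What is lost is the Week 12 and Week 20 values.
- **That Week 12 and Week 20 LUMT and SF-12 are the primary time points.** Sections 2.1 and 6.3.1 name the instruments without a time.
- **That the 12-week healing proportion is inflated.** With 17 evaluable patients, 3 leavers and 7 of the remaining 14 healed (all assumed), dropping the leavers gives 7/14 = 50.0% against 7/17 = 41.2%. That shift requires removing them from the denominator, which 7.1.1 does not suggest.

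**Conclusion.** The point holds in a limited form. Followed as written, the Protocol allows patients who meet criteria linked to poor healing to leave without a Week 12 or Week 20 wound, LUMT or SF-12 assessment. This bears on one secondary measure (Week 12 area reduction) and on the later values of two primary instruments.

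The total effect is unknown, because neither the number of withdrawals nor their outcomes can be derived from the Protocol. The illustration of 1.3 to 4.2 points per missing patient rests on an assumed D of 25 to 50 points and on n of 12 to 19; if leavers resemble those who stay, the shift is zero. No hypothesis test is affected. What is at stake is the efficacy signal taken into later studies. This is a cheap improvement rather than a defect that undermines the study, but it has to be made in the Protocol, since that is where data collection is set.

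**What to change.** In both 4.6.2 and 6.1.3, state that a patient meeting any of (i)-(iv) receives no further DermGEN but continues the scheduled wound measurement, photograph, LUMT and SF-12 assessments through Week 20 unless consent is withdrawn, and that any other wound treatment given is recorded. This extends the approach that section 3.2 already takes after a replacement graft.

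Replace the reference to 6.5.1: any exit visit follows the Week 20 content of 6.1.3, with SF-12 explicitly included.

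The cost is Protocol wording and a few visits that are already scheduled. Some patients may still not attend, later values may partly reflect other care (hence the record of other treatments), and the reported results may look slightly less favourable.

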6.1.4 Compliance

Patients will be required to attend all scheduled appointments required for the study. If required, appointments may be re-scheduled within a week of the original appointment date. Patients will be required to adhere to home care regimes as provided verbally and in writing by their clinician including dressing changes, off-loading of the affected limb, and immediate reporting of adverse events such as infection, continued bleeding, excessive inflammation and pain. Patients will be encouraged to take their own photographs of any untoward signs.

6.2 Safety Assessments

6.2.1 Physical Examination

A relevant physical examination assessing the subject's overall health and physical condition will be performed at every visit.

6.2.2 Adverse Events

All AEs occurring after the subject has signed the ICF until the end of the Follow-up period will be recorded. AEs present at first dosing or any AE identified prior to first dosing will be recorded in the source documentation as Baseline Signs and Symptoms.

AEs will be ascertained on the basis of volunteered signs or symptoms and on clinical observation and assessment at study visits. Spontaneous AEs will be recorded as such, and AEs will also be elicited by clinical site staff using non-leading questions at designated time points.

All SAEs will be followed until resolved or until a stable status has been achieved.

6.2.3 Clinical Laboratory Assessments

Patients must have recent HbA_{1c} data in order to qualify for enrollment, and be not excluded on other health grounds. A repeat HbA_{1c} will be obtained at the end of study (or withdrawal) visit for each patient, as well.

Other laboratory data obtained during the study as part of usual care should be available for audit by the sponsor during the study and for 6 months after; but no specific testing is required by this protocol.

Laboratory safety data will be reviewed by the investigator or designee as part of usual care.

6.2.4 Medication History

All medications (prescription and non-prescription, herbal medications, or investigational drugs) taken by the subjects during the 14 days prior to Screening and during the remainder of the study will be recorded in the source documentation. The reported medications will be reviewed and evaluated by the investigator or designee to determine if they affect the subject's eligibility to participate in the study.

6.2.5 Concomitant Medications

Patients will remain on all medications prescribed to treat their diabetes and associated conditions as determined at the time of enrolment. If there are any changes to a patient's medication (dosing, new medications, alternate medications) during the study, this will be noted in the patient's study file and reviewed by the study supervising clinician to determine continued eligibility of the patient in the study.

6.3 Efficacy Assessments

6.3.1 Primary Outcome Measurements are the following:

1. Mean and median reduction in wound area in the first 4 weeks
2. Proportion with complete healing in the first 12 weeks. (Complete healing is defined as 100% epithelialization without drainage.)
3. Incidence of adverse events
4. Impact of treatment, as measured by LUMT and SF-12.

6.3.1.1 Wound Size

Wound size will be assessed:

- a) By direct measurement of largest and smallest dimensions; and
- b) By estimation from a photograph with a measurement scale shown beside the wound. Photographs should be taken from a distance of approximately 6 inches, and from vertically above the centre of the ulcer.

6.3.1.2 Impact of Treatment

The impact of treatment will be analyzed using the LUMT and the Short-Form Health Survey (SF-12), both reliable and validated outcome measures.

The Leg Ulcer Measurement Tool (LUMT) provides numerical scale grading of clinician- and patient-rated domains (see Appendix 4).

The short form health survey (SF-12) is a 12-question assessment of mental and physical health and quality of life outcomes. (See Appendix 5)

6.3.2 Secondary Outcome Measurements include the following:

1. Time to complete healing
2. Time to first-measured complete healing
3. Incidence of recurrence after complete healing
4. Change in wound characteristics over time
5. Mean and median reduction in wound area at 12 weeks

7. DATA ANALYSIS AND STATISTICAL CONSIDERATIONS

7.1 Statistical and Analytical Plans

7.1.1 Analysis Populations

Safety population: all subjects will be included in the analysis for safety.

Efficacy population: all subjects excepting the first 1 to 3 (i.e. those treated before standardization of procedures) will be included in the analysis to seek efficacy signals.

7.1.2 General Statistical Considerations

This small study is not expected to support statistical conclusions. Descriptive statistics will be used throughout.

7.1.3 Planned Analyses

7.1.3.1 Analysis of Safety Assessments

Safety data include treatment-emergent AEs, physical exams, and clinical laboratory assessments.

Narrative summary reports will constitute the adverse event database, with simple summary analysis. Systemic effects are not expected due to DermGEN alone, and such AE's may be expected to be caused by the underlying ulcer. All serious AE's will be reported as required by GCP, and will be described in full in the final study report.

7.1.3.2 Analysis of Efficacy Assessments

Photographic, narrative, and laboratory data will be examined in various ways to seek a signal of efficacy. Conclusions may be used to design more rigorous efficacy investigations in one or more subsequent studies.

7.1.3.3 Demographics and Other Baseline Characteristics

Demographic and baseline characteristics will include age, ethnic origin, height, weight, and BMI. Other baseline information will include relevant medical and surgical history, and prior and concomitant medications. Descriptive statistics (number of subjects, mean, standard deviation, median, minimum and maximum) for continuous variables, and the proportion of subjects for categorical variables will be

presented for demographic and baseline characteristics using the safety population. No formal statistical comparison between the groups will be performed.

All important deviations related to study inclusion or exclusion criteria, conduct of the trial, subject management, or subject assessment will be described. Relevant medical and surgical history will be listed.

7.2 Determination of Sample Size

The sample size chosen for this study was based upon precedent set by other first in human studies of similar nature and was not based on power calculations.

8. STUDY ADMINISTRATION

8.1 Data Collection and Database Construction

For all data collected on the CRF, source documentation should be available at the site. A source document checklist will be used to identify the source data for all data points collected.

For the clinical trial, DeCell Technologies will assign a unique identifier for each patient enrolled in the study and this identifier will be used on all Case Report Forms (CRFs) and any other documents sent to DeCell throughout the study. Information collected under the unique identifier for each patient will be devoid of any specific personal information that may directly identify an individual. Only each clinician's study coordinator and the clinicians themselves participating in the study will know the identity of their patients and their assigned unique study identifier for traceability. DeCell Technologies will know the unique patient identifier and unique product code of decellularized skin used to treat the patient for traceability. Data for the study will be captured on a paper version of CRFs and sent to DeCell Technologies who will enter all the data into an electronic database created in Microsoft Excel® that will be encrypted with a password. Access to the database will only be made available to the Halifax-based Study Coordinator, the P.I. of each participating site, and DeCell Technologies Inc.

8.2 Regulatory and Ethical Considerations

8.2.1 Ethical Conduct of the Study

This study will be conducted in accordance with GCP and all applicable regulations, including, where applicable, the Declaration of Helsinki. The study will also be carried out in keeping with applicable local laws and regulations. This may include an inspection by the sponsor representatives and/or regulatory authority representatives at any time.

8.2.2 Notification to Primary Care Physician

If agreed to by the subject, the investigator or designee will notify the subject's primary care physician of the subject's participation in the study. The primary care physician may contact the investigator for any further information regarding the subject's participation in the study.

8.2.3 Regulatory Authority Approval

In accordance with any applicable local regulations, the sponsor or designee will obtain approval from the appropriate regulatory agency prior to a site initiating the study in that country or jurisdiction.

